5.2. Inclusion Criteria

A subject will be eligible for inclusion in this study only if all of the following criteria apply:

AGE

1. \geq 18 years of age, at the time of signing the informed consent.

TYPE OF SUBJECT AND DIAGNOSIS INCLUDING DISEASE SEVERITY

- 2. **Hemoglobin**: Stable Hgb 9.0 11.5 g/dL (see Section 5.1).
- 3. **Dialysis frequency**: On hemodialysis (HD, hemofiltration or hemodiafiltration) three to five times weekly for at least 4 weeks prior to Day -28 Screening through Day 29.
- 4. **Dialysis adequacy**: A single pool Kt/V_{urea} of ≥1.2 based on a historical value obtained within the prior three months in order to ensure the adequacy of dialysis. If Kt/V_{urea} is not available, then an average of the last 2 values of urea reduction ratio (URR) of at least 65%. **NOTE**: Only needs confirming at Day -28.
- 5. **Stable ESA dose**: Treated with the same ESA (epoetins or their biosimilars, or darbepoetin or methoxy PEG-epoetin beta) with total weekly dose varying by no more than 50% from 4 weeks prior to Day -28 through Day 1 (randomization).
- 6. **Iron replacement therapy**: Subjects may be on maintenance oral or IV iron

supplementation. If subjects are on oral iron, then the type of iron and doses must not be changed for the 4 weeks prior to Day -28, during the screening phase, and through the 29 days of treatment. If subjects are on IV iron, then doses must be ≤100 mg/week, and doses must not be changed for the 4 weeks prior to Day -28, during the screening phase, and through the 29 days of treatment.

INFORMED CONSENT

7. Capable of giving signed informed consent as described in Section 10.2, which includes compliance with the requirements and restrictions listed in the consent form and in this protocol.

5.3. Exclusion Criteria

A subject will not be eligible for inclusion in this study if any of the following criteria apply:

CKD-RELATED CRITERIA

- 1. **Dialysis modality**: Planned change from HD to peritoneal dialysis within the study time period.
- 2. **Renal transplant**: Planned for living-related or living-unrelated kidney transplant.
- 3. **High ESA dose**: An epoetin dose of ≥360 IU/kg/week IV or ≥250 IU/kg/week subcutaneous (SC) or darbepoetin dose of ≥1.8 µg/kg/week IV or SC or methoxy PEG-epoetin beta dose of ≥2.2 µg/kg/week within the prior 8 weeks through Day 1 (randomization).
- 4. **Mircera**: Administration of Mircera (methoxy PEG-epoetin beta) within 2 weeks prior to Day 1 if subject is on a once-every-2-weeks schedule or within 4 weeks prior to Day 1 if subject is on a once-every-4-weeks schedule.

CARDIOVASCULAR DISEASE-RELATED CRITERIA

- 5. **Myocardial infarction or acute coronary syndrome:** Within the 8 weeks prior to Screening through Day 1 (randomization).
- 6. **Stroke or transient ischemic attack:** Within 8 weeks prior to Screening through Day 1 (randomization).
- 7. **Heart failure:** Class IV heart failure, as defined by the New York Heart Association (NYHA) functional classification system diagnosed prior to Screening through Day 1 (randomization).
- 8. **QTcB:** QTcB >500 msec or QTcB >530 msec in subjects with Bundle Branch Block. There is no QTc exclusion for subjects with a predominantly paced rhythm.

OTHER DISEASE-RELATED CRITERIA

- 9. **Inflammatory disease:** Active chronic inflammatory disease that could impact erythropoiesis (e.g., scleroderma, systemic lupus erythematosis, rheumatoid arthritis, celiac disease) diagnosed prior to Screening through Day 1 (randomization).
- 10. **Hematological disease**: Any hematological disease including those affecting platelets, white or red blood cells (e.g., sickle cell anemia, myelodysplastic syndromes, hematological malignancy, myeloma, hemolytic anemia and thalassemia), coagulation disorders (e.g., antiphospholipid syndrome, Protein C or S deficiency), or

- any other cause of anemia of chronic disease other than renal disease diagnosed prior to Screening through Day 1 (randomization).
- 11. **Liver disease:** Current liver disease, known hepatic or biliary abnormalities (with the exception of Gilbert's syndrome or asymptomatic gallstones) or evidence at Screening of abnormal liver function tests [alanine transaminase (ALT) or aspartate transaminase (AST) >2x upper limit of normal (ULN) or total bilirubin >1.5xULN]; or other hepatic abnormalities that in the opinion of the investigator would preclude the subject from participating in the study.
 - **NOTE:** Those with Hepatitis B or Hepatitis C are eligible provided these exclusions are not met.
- 12. **Major surgery:** Major surgery (excluding vascular access surgery) within the 8 weeks prior to Screening, during the Screening phase, or planned during the study.
- 13. **Transfusion:** Blood transfusion within the 8 weeks prior to Screening, during the Screening phase or an anticipated need for blood transfusion during the study.
- 14. **GI Bleeding:** Evidence of actively bleeding peptic, duodenal, or esophageal ulcer disease **OR** clinically significant GI bleeding within the 8 weeks prior to Screening through Day 1 (randomization).
- 15. **Acute Infection:** Clinical evidence of acute infection or history of infection requiring intravenous (IV) antibiotic therapy within the 4 weeks prior to Screening through Day 1 (randomization). **NOTE:** IV antibiotics as prophylaxis are allowed.
- 16. **Malignancy:** History of malignancy within the two years prior to Day -28 through to Day 1 (randomization) or currently receiving treatment for cancer, or has a known complex kidney cyst (i.e. Bosniak Category II F, III of IV) > 3cm. **NOTE:** The ONLY exception is squamous cell or basal cell carcinoma of the skin that has been definitively treated ≥ 8 weeks prior to Screening.

CONCOMITANT MEDICATIONS

- 17. **Severe allergic reactions:** History of severe allergic or anaphylactic reactions or hypersensitivity to excipients in the investigational product.
- 18. **Drugs and supplements:** Use of any prescription or non-prescription drugs or dietary supplements that are prohibited (see Section 6.9.2 for details) from Screening until the Follow-up Visit.
- 19. **Prior investigational product exposure**: The Subject has participated in a clinical trial and has received an experimental investigational product within the prior 30 days from Screening through Day 1 (randomization).

GENERAL HEALTH RELATED CRITERIA

- 20. **Other conditions:** Any other condition, clinical or laboratory abnormality, or examination finding that the investigator considers would put the subject at unacceptable risk, which may affect study compliance or prevent understanding of the aims or investigational procedures or possible consequences of the study.
- 21. **Females ONLY:** Does not meet the female eligibility criteria (Section 12.6 Appendix 6), is pregnant [as confirmed by a positive serum human chorionic gonadotrophin (hCG) test for females of reproductive potential (FRP) only], breastfeeding, and if of reproductive potential does not agree to follow one of the options listed in Section 12.6.1.

DIAGNOSTIC ASSESSMENTS AND OTHER CRITERIA

(To be verified on Day -28 only)

- 22. **Vitamin B₁₂:** At or below the lower limit of the reference range (may rescreen in a minimum of 8 weeks).
- 23. Folate: <2.0 ng/mL (4.5 nmol/L) (may rescreen in a minimum of 4 weeks).
- 24. **Ferritin:** <100 ng/mL (<100 µg/L).
- 25. Transferrin saturation (TSAT): <20%.

5.4. Other Eligibility Criteria Considerations

Laboratory eligibility criteria will be assessed according to the central laboratory results from the Screening visit samples. See Section 7.4.6 for a listing of Clinical Laboratory Assessments.

5.5. Screening/Baseline/Run-in Failures

Screen failures are defined as subjects who consent to participate in the clinical trial but are never subsequently randomized. In this study, a subject can become a screen failure at any time from the Day -28 visit to the Day 1 visit, prior to randomization. In order to ensure transparent reporting of screen failure subjects, meet the Consolidated Standards of Reporting Trials (CONSORT) publishing requirements, and respond to queries from Regulatory authorities, a minimal set of screen failure information is required including Demography, Screen Failure details, Eligibility Criteria, and Serious Adverse Events (see Section 7.4.1.6).

Subjects who fail screening may be rescreened as soon as the investigator feels they may have become eligible. However, an individual subject may not rescreen more than twice. There is no predetermined amount of time that the investigator needs to wait to rescreen a previously ineligible subject, except those excluded for Hgb or folate who may only rescreen in 2 and 4 weeks, respectively, and those excluded for Vitamin B_{12} who may rescreen in 8 weeks.

5.6. Withdrawal/Stopping Criteria

A subject may withdraw from study treatment at any time at his/her own request, or may be withdrawn at any time at the discretion of the investigator for safety, behavioral or administrative reasons. If a subject withdraws from the study, he/she may request destruction of any samples taken, and the investigator must document this in the site study records.

The reason for discontinuation of study treatment and/or withdrawal from the study must be recorded in the eCRF.

Refer to the Time and Events Table (Section 7.1) for the assessments to complete in the event of discontinuation of study medication and early withdrawal.

5.6.1. Criteria for Permanent Discontinuation from Study Medication and Early Withdrawal

Subjects must **permanently discontinue study medication** for the following reasons:

- Meeting Hgb stopping criteria (Section 5.6.2).
- Receiving blood transfusions.
- Receiving kidney transplant.
- Subject becomes pregnant or intends to become pregnant during the study.
- Active GI bleeding.
- Diagnosis of cancer, with the exception of squamous cell and basal cell carcinoma.
- Liver chemistry abnormalities exceeding the threshold criteria (Section 5.6.4).
- Missing 2 consecutive dialysis sessions.
- Need for chronic (more than 14 days) use of prohibited medication (Section 6.9.2).

The subject should attend the clinic as soon as possible to complete the Early Withdrawal assessments and return for a Follow-up visit as described in Section 7.1, Time and Events.

The reason for discontinuation of study medication and date of last dose will be recorded in the eCRF.

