7.4.1.1. Time period and Frequency for collecting AE and SAE information

- Any SAEs assessed as related to study participation (e.g., protocol-mandated procedures, invasive tests, or change in existing therapy) or related to a GSK product will be recorded from the time a subject consents to participate in the study up to and including any follow-up contact.
- AEs will be collected from the start of Study Treatment (Day 1) until the Follow-up visit (see Section 7.4.1.4).
- Medical occurrences that begin prior to the start of study treatment but after obtaining informed consent may be recorded on the Medical History/Current Medical Conditions section of the eCRF.
- All SAEs will be recorded and reported to PPD within 24 hours, as indicated in Section 12.5.4.
- Investigators are not obligated to actively seek AEs or SAEs in former study subjects. However, if the investigator learns of any SAE, including a death, at any time after a subject has been discharged from the study, and he/she considers the event reasonably related to the study treatment or study participation, the investigator must promptly notify PPD.

NOTE: The method of recording, evaluating and assessing causality of AEs and SAEs plus procedures for completing and transmitting SAE reports to PPD are provided in Section 12.5.6.

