Death, MI, stroke, congestive heart failure, venous thromboembolism, thrombosis of vascular access at Hgb levels which are within the normal range (i.e. not polycythemic conditions)	Marketed rhEPO/ESAs have been associated with an increased risk for death and serious cardiovascular events when used in patients with anemia of CKD. Following review of clinical data received to date, this has not been identified as a safety concern for GSK1278863.	 Specific eligibility criteria related to CV risk are outlined in Section 5.3 Hgb will be closely monitored throughout the dosing period as outlined in the Time and Events Table (Section 7.1) Blinded monitoring of emerging safety data by an internal GSK Safety Review Team
Cancer-related mortality and tumor progression and recurrence	In clinical trials, use of rhEPO in patients with cancer has been associated with increased risk of cancer related morbidity and mortality. Administration of 60mg/kg GSK1278863 to mice caused minimal increases in circulating VEGF while significant EPO increases were observed. In clinical studies up to 4 weeks duration, a dose-ordered increase in VEGF plasma concentrations, an angiogenic factor that has been implicated in tumor growth, was observed at doses ranging from 10 to 150 mg. In clinical studies up to 24 weeks duration at doses up to 25 mg, changes in VEGF plasma concentrations were variable but similar relative to control. Following review of clinical data received to date, this has not	 Specific eligibility criteria related to cancer risk are outlined in Section 5.3 Stopping criteria for subjects with treatment emergent malignancy are outlined in Section 5.6.1 Blinded monitoring of emerging safety data by an internal GSK Safety Review Team

Potential Risk of Clinical Significance	Summary of Data/Rationale for Risk	Mitigation Strategy
	been identified as a safety concern for GSK1278863.	
Pulmonary artery hypertension (PAH)	A role for HIF-regulated pathways in the pathophysiology of PAH has been suggested based on well established effects of acute and chronic hypoxia in man on the pulmonary vasculature (vasoconstriction), and by findings in patients with naturally occurring mutations that result in decreased HIF degradation [Smith, 2006; Formenti, 2011].	Blinded monitoring of emerging safety data by an internal GSK Safety Review Team

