- Examples of such events are invasive or malignant cancers, intensive treatment in an emergency room or at home for allergic bronchospasm, blood dyscrasias or convulsions that do not result in hospitalization, or development of drug dependency or drug abuse.

g. Is associated with liver injury and impaired liver function defined as:

- ALT \geq 3xULN and total bilirubin* \geq 2xULN (>35% direct), or
- ALT \geq 3xULN and INR** \geq 1.5.
- * Serum bilirubin fractionation should be performed if testing is available; if unavailable, measure urinary bilirubin via dipstick. If fractionation is unavailable and ALT \geq 3xULN and total bilirubin \geq 2xULN, then the event is still to be reported as an SAE.
- ** INR testing not required per protocol and the threshold value does not apply to subjects receiving anticoagulants. If INR measurement is obtained, the value is to be recorded on the SAE form.
- Refer to Section 12.2 Appendix 2 for the required liver chemistry follow-up instructions

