 - a. For a subject who receives dialysis 3-5 times per week and starts dosing on Monday or Tuesday, the expected dose days are: 1, 3, 5, 8, 10, 12, 15, 17, 19, 22, 24, 26, and 29.
 - b. For a subject who receives dialysis 3-5 times per week and starts dosing on Wednesday or Thursday, the expected dose days are: 1, 3, 6, 8, 10, 13, 15, 17, 20, 22, 24, 27, and 29.
 - c. For a subject who receives dialysis 3-5 times per week and starts dosing on Friday or Saturday, the expected dose days are: 1, 4, 6, 8, 11, 13, 15, 18, 20, 22, 25, 27, and 29.
2. Determine the “expected cumulative number of tablets” by comparing the last dose day (last dose date – first dose date +1) with the expected dose days. For example, for a subject who received dialysis 3 times per week and started dosing on Wednesday, if the subject’s last dose day is day 7, then the expected cumulative number of tablets taken from a bottle should be 3 (because the last dose was administered before the fourth dose day); if the subject’s last dose day is day 8, then the expected cumulative number of tablets taken from a bottle should be 4 (because the last dose was administered on the fourth dose day).
3. For all other situations which is not covered in step “1” (i.e. a subject who does not receive dialysis 3-5 times per week and/or does not start dosing on Monday – Saturday), the following formula will be used to estimate the “expected cumulative number of tablets” taken from each bottle during the treatment period:

$$\text{Expected cumulative number of tablets} = \text{round}((i - 1) * 3/7, 1) + 1$$

Where “i” is the “last dose day”.

Overall compliance for a subject is categorized as follows: >0% and <80% if compliance for at least one bottle is <80%, 80% to 120% if compliance for all three bottles is between 80% and 120%, and >120% otherwise.

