11.1.2. Exclusions from Per Protocol Population

The following criteria define the protocol deviations, which may lead to the exclusion of a subject from the per protocol (PP) population (refer to Section 4 for population definitions). These are the deviations that are considered to affect interpretation of the primary endpoint (Hgb change from baseline at Day 29). Protocol deviations will be recorded and documented in the PPD's protocol deviation capturing tool. Potential protocol deviations listed below will be reviewed by the clinical team to establish whether subjects meeting these criteria should be excluded from the PP population. This review will occur before the clinical database has been locked for the final analysis.

Number	Exclusion Description
01	Inclusion/Exclusion criteria not met. 
 Subjects who deviate from any inclusion or exclusion criteria, as recorded in the eCRF)
02	Not withdrawn after meeting the following stopping criteria prior to Day 29 
 receiving blood transfusion receiving kidney transplant having active GI bleed liver stopping criteria patient not discontinued from the study treatment despite having missed two or more consecutive dialysis sessions diagnosis of cancer, with the exception of squamous cell and basal cell carcinoma pregnancy
03	Prohibited medication taken during study treatment phase, prior to Day 29 
 Subject taking single dose of long-acting darbepoetin or Mircera during the study (Day 1 – Day 29) Subject taking more than one dose of Epoetin, or more than 2 non-consecutive Epoetin administrations

Number	Exclusion Description
	
 Subject taking the prohibited medications (inhibitor or inducer of CYP2C8: gemfibrozil and rifampin/rifampicin) during the 29-day study treatment phase and 7 days after last dose of study treatment).

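### The mandatory cancer stop in Protocol 5.6.1 exempts squamous and basal cell carcinoma without limiting the exemption to the skin

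*Protocol*

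**What the plan says.** Section 5.6.1 of the Protocol is a mandatory list: a subject who meets any item must permanently discontinue study medication. The cancer item reads "Diagnosis of cancer, with the exception of squamous cell and basal cell carcinoma". It has no site qualifier.

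The same two tumour types appear in exclusion criterion 16 (Section 5.3), which bars subjects with recent malignancy or current cancer treatment. There the exception is narrower: "The ONLY exception is squamous cell or basal cell carcinoma of the skin that has been definitively treated ≥ 8 weeks prior to Screening".

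The risk table in Appendix 3 (Section 12.3) relies on the stopping rule as a precaution against cancer-related risk: "Stopping criteria for subjects with treatment emergent malignancy are outlined in Section 5.6.1". That row gives two other mitigations, the eligibility criteria and blinded monitoring by the internal Safety Review Team.

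SAP Section 11.1.2, item 02, lists failures to withdraw a subject after certain stopping criteria were met. Its cancer entry repeats the Protocol's exception, again with no site: "diagnosis of cancer, with the exception of squamous cell and basal cell carcinoma".

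**The concern.** Squamous cell carcinoma is not only a skin tumour; it also arises in the lung, the head and neck and the esophagus. An exemption written by cell type alone therefore covers invasive cancers that a rule of this kind would be expected to catch. As the text stands, a subject with a recent squamous lung cancer could not enter the trial, yet a subject diagnosed with one during treatment need not stop. The documents give no reason for the exemption to be wider on treatment than at entry.

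What is at stake is a stated safety precaution. Cancer-related mortality and tumour progression or recurrence is an adverse event of special interest (Section 7.4.1.2), and Appendix 3 names the stop in Section 5.6.1 as one of three mitigations. Appendix 3 also says that review of clinical data to date has not identified cancer as a safety concern. The point is thus a gap in a precaution and not evidence of harm.

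**Working it through.** The plan states no figure to reproduce. The check has two parts: a comparison of the provisions that bear on the rule, and a bound on the exposure involved.

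**Comparison of provisions**

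| Provision | Site limit on the exception? | Does it require stopping for a new non-skin squamous carcinoma? |
|---|---|---|
| Protocol 5.6.1, cancer item | None | No; the tumour falls inside the exemption |
| Protocol 5.3, exclusion 16 | Skin only | Not applicable; governs entry |
| Protocol 12.3, cancer row | None; points back to 5.6.1 | No |
| Protocol 5.6, general withdrawal | Not applicable | No; a subject "may be withdrawn at any time at the discretion of the investigator for safety, behavioral or administrative reasons" |
| Protocol 12.5.2, serious adverse events | Not applicable | No; it classifies the event: "Examples of such events are invasive or malignant cancers" |
| Protocol 7.4.1.1, reporting | Not applicable | No; it makes the event visible: "All SAEs will be recorded and reported to PPD within 24 hours" |
| SAP 11.1.2, item 02 | None | No; it concerns the per-protocol population |

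Only the site wording of exclusion 16 can be compared with Section 5.6.1. Its requirement of definitive treatment at least 8 weeks before Screening concerns history at entry and cannot apply to a new on-study diagnosis.

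Other items in Section 5.6.1, such as active GI bleeding or transfusion, might apply to the same patient. They would do so because of the bleeding or transfusion, not because of the cancer.

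**Size**

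Inputs: about 90 randomized subjects, 18 per arm (Protocol 9.2); four active arms with a top dose of 30 mg (Protocol 4.2); a 29-day treatment period; 13 scheduled doses (SAP 6.2.6).

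- Planned exposure, all arms: 90 × 29 / 365.25 = 7.15 patient-years.
- Planned exposure, active arms: 4 × 18 = 72 subjects; 72 × 29 / 365.25 = 5.72 patient-years.

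These figures assume that every randomized subject is treated for the full 29 days.

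SAP 6.2.6 gives three dosing calendars according to the starting weekday. For a Monday or Tuesday start, "the expected dose days are: 1, 3, 5, 8, 10, 12, 15, 17, 19, 22, 24, 26, and 29". Doses remaining after Day 15 are:

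- Monday or Tuesday start: Days 17, 19, 22, 24, 26, 29 = 6 doses.
- Wednesday or Thursday start: Days 17, 20, 22, 24, 27, 29 = 6 doses.
- Friday or Saturday start: Days 18, 20, 22, 25, 27, 29 = 6 doses.

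So 6 of 13 doses remain under each calendar. In the top-dose arm that is 6 × 30 mg = 180 mg. The figure applies to one hypothetical subject diagnosed at Day 15 whose dosing is not otherwise stopped. It is not an expected harm, because the documents give no incidence from which to derive one.

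**The case against.** The strongest reply is that the intent is plain. Basal cell carcinoma is a skin tumour, so the pair reads naturally as shorthand for the common non-melanoma skin cancers, and exclusion 16 spells the site out. On this view the text is ambiguous rather than wrong. It causes trouble only if a site reads Section 5.6.1 in isolation, treats a new lung or esophageal carcinoma as exempt, and chooses to keep dosing. Nothing in the Protocol tells anyone to continue. The investigator can withdraw a subject for safety at any time, the event would be handled as a serious adverse event, events of special interest must be followed up (Section 7.4.1.4), and the Safety Review Team watches accruing data. Active GI bleeding would stop some esophageal cases anyway.

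The SAP aspect is also slight. Item 02 lists deviations that may lead to exclusion after clinical review, and the per-protocol population is not analysed if it exceeds 80% of the ITT population.

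Most of this stands, and it limits the consequence. The intended meaning can probably be recovered, and whether the omission was an oversight or accepted shorthand cannot be settled from the documents. It does not close the gap. Reporting, follow-up and blinded monitoring do not require stopping, and withdrawal under Section 5.6 is discretionary. A mandatory list exists so that stopping does not depend on reading a qualifier across from an eligibility criterion.

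**Conclusion.** The concern holds, at minor severity. On its literal text the cancer stop does not cover a new squamous cell carcinoma outside the skin, and no other provision makes stopping mandatory for that diagnosis. The exemption removes the automatic stop; it does not direct continued dosing. The likely explanation is an editorial omission, but that is an inference.

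The event should be rare in about 7.1 planned patient-years of treatment, although its expected number cannot be stated. The primary dose-response analysis is unaffected. The conclusion rests on the wording of the current Protocol and SAP, not on any assumption about how sites would behave.

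**What to change.** In Protocol Section 5.6.1, add the words 'of the skin' after 'carcinoma' in the cancer item, so that the exemption covers only squamous cell or basal cell carcinoma of the skin. Make the same edit in SAP Section 11.1.2, item 02, so that a failure to stop in such a case is caught as a potential per-protocol deviation. Do not import the 8-week definitive-treatment condition from exclusion 16. Appendix 3 needs no change, since it refers to Section 5.6.1.

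The cost is three words in each document, with no additional patients, visits or analyses.
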